12.6 Physical Examination

12.6.1 Parameters

- Gastrointestinal (GI)
- Cardiovascular
- Dermatological
- Extremities
- General appearance
- HEENT (Head, Eyes, Ears, Nose, Throat)
- Renal
- Musculoskeletal
- Neurological
- Respiratory
- Thyroid
- Other (free text)

12.6.2 Biostatistical methods

Physical examination data will be listed for all participants by scheduled visit.

12.7 12-Lead ECG

12.7.1 Parameters

- The following ECG parameters are collected in triplicate for each timepoint:
 - PR interval (msec)
 - QRS interval (msec)
 - QT interval (msec)
 - Heart rate (beats/minute)
 - QTcB Interval (msec)
 - QTcF Interval (msec)
- ECG result (Normal, Abnormal – Not clinically significant, Abnormal – Clinically significant)
- ECG abnormality (as appropriate)

12.7.2 Biostatistical methods

ECG parameters will be listed for all participants and time points.

Observed values, and absolute change from baseline, will be summarised descriptively for all ECG parameters by scheduled visit and timepoint for part A and by sequence and overall for part B.

The number and percentage of participants with ECG findings will also be summarized by scheduled visit and timepoint part A and by sequence and overall for part B. This table will include a summary of the number and percentage of participants with abnormal results for each parameter at each timepoint, using the set of normal ranges provided.

A maximum shift table will also be presented for ECG Result, presenting a summary of the shifts from baseline values to the most extreme post-baseline value, where all scheduled and unscheduled visit results will be assessed to determine the maximum shift, ordered (best to worst case) by Normal, Abnormal – NCS, Abnormal – CS.

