# 21. STATISTICAL ANALYSIS

## 21.1. General considerations

An analysis of Part A will be conducted when all subjects in Part A have completed Part A.

A final analysis of Part B will be conducted when all subjects have completed Part B.

The statistical analysis principles described below will be supplemented by a comprehensive statistical analysis plan (SAP) which will be finalised before the database is locked. This will contain details of methods for handling missing data and early withdrawals. Any changes to the statistical analysis plan will be described and justified in the final report.

Descriptive statistics will be used to analyse the data in both Part A and Part B of the study. The descriptive summary for the categorical variables will include counts and percentages. The descriptive summary for the continuous variables will include number of participants (n), means, medians, standard deviations, and minimum and maximum values. Pharmacokinetic measures will be analysed as for continuous variables.

In Part A and Part B, data will be tabulated and analysed with respect to subject enrolment and disposition.

In Part A, demographic, baseline characteristics and prior medications summaries will be presented overall. Concomitant medications, PD, PK and safety measure summaries will be presented by active treatment dose, placebo and overall. Note that results for the subjects on placebo across all doses will be combined for summary purposes.

---

In Part B, demographic, baseline characteristics (including history of lumbar radicular pain) and prior medications will be presented by treatment sequence and overall. Efficacy, PD, PK, concomitant medications and safety measure summaries will be presented by treatment within each treatment period and overall.

As this is a Proof-of-Concept study, no formal statistical hypotheses are being specified although some may be investigated as part of the data presentation, in which case corresponding 95% confidence intervals will be presented for treatment differences and p-values of  $<0.05$  will be declared statistically significant. Treatment comparisons will take into account the paired nature of the treatment responses where feasible and treatment period order will be ignored in any treatment comparisons.

All data will be listed for all subjects to support each table and to present all data. All statistical analyses will be performed using SAS unless otherwise stated in the SAP.

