### 21.3. Analysis of safety data

Safety observations and measurements include study drug exposure, AEs, safety laboratory tests, vital signs, physical examinations and ECGs.

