#### 21.3.4. Other safety measures

Individually for Part A and Part B:

- Vital signs (body temperature, respiratory rate, heart rate, and blood pressure) will be summarised by baseline and treatment overall and for each treatment within the treatment sequence. Changes over time in vital signs will be summarised.
- Physical examination data will be listed only.
- The number and percentage of participants receiving concomitant medications will be tabulated overall and by medication received.

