3.2.6 Treatment groups – Part B

LAT8881 will be administered at a dose of 1.8 mg/kg via an infusion pump at a constant rate over 10 minutes.

The placebo formulation will be presented as above but without the LAT8881 active.

Tabulations for part 2 will summarise data as follows:

Demographics and baseline characteristic data, will be summarised by:

- LAT8881 1.8 mg/kg /Placebo
- Placebo/LAT8881 1.8 mg/kg
- Total

Visit based tabulations will be summarised by treatment received (LAT8881 1.8 mg/kg or Placebo) and total, and timepoint relative to within period dosing. Treatment will be assigned to individual records based on the treatment period. Timepoints will be:

- Screening (summarised as total only)
- Day 1- predose/Day 2-predose (combination of Day 1 and Day 2, summarised by treatment)
- Day 1- dose/Day 2-dose (combination of Day 1 and Day 2, summarised by treatment)
- Day 1- 5min/Day 2-5min (combination of Day 1 and Day 2, summarised by treatment)
- Day 1- 10min/Day 2-10min (combination of Day 1 and Day 2, summarised by treatment)
- Day 1- 15min/Day 2-15min (combination of Day 1 and Day 2, summarised by treatment)
- Day 1- 20min/Day 2-20min (combination of Day 1 and Day 2, summarised by treatment)
- Day 1- 30min/Day 2-30min (combination of Day 1 and Day 2, summarised by treatment)
- Day 1- 45min/Day 2-45min (combination of Day 1 and Day 2, summarised by treatment)
- Day 1- 1hr/Day 2-1hr (combination of Day 1 and Day 2, summarised by treatment)
- Day 1- 1.5hr/Day 2-1.5hr (combination of Day 1 and Day 2, summarised by treatment)
- Day 1- 2hr/Day 2-2hr (combination of Day 1 and Day 2, summarised by treatment)
- Day 1- 2.5hr/Day 2-2.5hr (combination of Day 1 and Day 2, summarised by treatment)
- Day 1- 3hr/Day 2-3hr (combination of Day 1 and Day 2, summarised by treatment)
- Day 1- 3.5hr/Day 2-3.5hr (combination of Day 1 and Day 2, summarised by treatment)
- Day 1- 4hr/Day 2-4hr (combination of Day 1 and Day 2, summarised by treatment)
- Day 1- 5hr/Day 2-5hr (combination of Day 1 and Day 2, summarised by treatment)
- Day 1- 6hr/Day 2-6hr (combination of Day 1 and Day 2, summarised by treatment)
- Day 9/ETV (summarised as total only)

○ Event based tabulations (e.g. adverse events, concomitant medications and deviations) will be summarised by treatment and total. Treatment will be assigned to individual records based on the treatment period of the start date of the event.

- Adverse Events:

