12.1 Adverse Events (AEs)

AEs will be coded using the current version of the Medical Dictionary for Regulatory Activities (MedDRA, version 24.1) by system organ class (SOC) and preferred term (PT), classified from verbatim terms.

All AEs recorded during the study will be listed, grouped by participant and treatment group.

A Treatment Emergent Adverse Event (TEAE) is defined as any untoward medical occurrence reported or observed after the start of dosing with study drug and prior to the End of Study visit. Conditions present before the first dose of study drug that increase in severity after the first study drug administration will also be considered TEAEs. Where an AE start date is partially or fully missing, and it is unclear as to whether the AE started after treatment administration, it will be assumed to be a TEAE.

AE summaries will be restricted to TEAEs only.

An overview summary table of TEAEs will be provided for:

- Part A by treatment group and overall
- Part B by treatment within sequence, by treatment and overall

Table will include number of participants reporting at least one of the following:

- TEAE
- Grade 3+ TEAE
- Related TEAE
- Serious TEAE
- Serious and related TEAE

Number of participants discontinued from treatment due to a TEAE

Number of participants withdrawn from the study due to a TEAE

Number of deaths

For the TEAE summaries, participants who experience the same TEAE more than once will be counted only once for that event within each category (PT, SOC or overall).

The number and percentage of participants experiencing a TEAE, will be summarised for each SOC and PT by cohort and overall for the following categories of events, by severity:

- All TEAEs
- All TEAEs related to the study drug
- All Grade 3+ TEAEs
- All serious TEAEs
- All serious TEAEs related to the study drug

The number and percentage of participants experiencing a TEAE will be summarised for each SOC and PT by maximum severity and cohort for all TEAEs and all TEAEs related to study medication. If a participant experiences the same AE at more than one severity grade, the most severe rating or the stronger causal relationship to investigational product will be given precedence. Only severities that are populated will be reported.

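### SAP 12.7.2 tabulates Part B ECG data by sequence, which leaves no LAT8881 or placebo column and conflicts with protocol 21.1 and SAP 3.2.6 and 12.2

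*SAP*

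**What the plan says.** SAP 12.7.2 describes three ECG tables.

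- Observed values and changes from baseline are summarised "by scheduled visit and timepoint for part A and by sequence and overall for part B".
- Abnormal findings follow the same split: "participants with ECG findings will also be summarized by scheduled visit and timepoint part A and by sequence and overall for part B".
- A maximum-shift table runs from baseline to the most extreme later result, "where all scheduled and unscheduled visit results will be assessed to determine the maximum shift". No columns are named for it.

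The general rules for Part B are different.

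- Protocol 21.1: "Efficacy, PD, PK, concomitant medications and safety measure summaries will be presented by treatment within each treatment period and overall". Protocol 21.3 makes ECG one of these measures: "Safety observations and measurements include study drug exposure, AEs, safety laboratory tests, vital signs, physical examinations and ECGs".
- SAP 3.2.6: "Visit based tabulations will be summarised by treatment received (LAT8881 1.8 mg/kg or Placebo) and total, and timepoint relative to within period dosing". That section gives sequence columns to demographics, baseline characteristics and treatment exposure, and does not mention ECG.
- SAP 12.2, in the section on medications, repeats the protocol 21.1 rule for safety measures.

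SAP 2.5 lists the Part B changes from the protocol. None concerns ECG.

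**The concern.** In a two-treatment, two-period crossover, a sequence column is not a treatment column. Participants in either sequence receive both LAT8881 and placebo, so someone who programs 12.7.2 as written produces a table in which neither treatment has a column of its own.

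Confirming safety in patients is a secondary objective of Part B, and protocol 5.2 reports mild ECG changes after LAT8881 in two earlier studies, one of them judged possibly related. A safety reader will look for ECG change on LAT8881 beside ECG change on placebo. Under 12.7.2 that comparison has to be rebuilt from sequence and day, if the rows allow it.

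**Working it through.** The plan gives no figure to reproduce, because the point is about table layout. The check compares the instructions and then works through what each layout can show.

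**1. Instructions for Part B, side by side**

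| Place | Data | Grouping |
|---|---|---|
| Protocol 21.1 with 21.3 | Safety measures, including ECG | Treatment within period, and overall |
| SAP 3.2.6 | Visit-based tables | Treatment received, and total |
| SAP 12.2 | Safety measures | Treatment within period, and overall |
| SAP 12.3.2 | Laboratory | Visit and treatment |
| SAP 12.1 | Adverse events | "Part B by treatment within sequence, by treatment and overall" |
| Protocol 21.3.4 | Vital signs | "will be summarised by baseline and treatment overall and for each treatment within the treatment sequence" |
| SAP 3.2.6 | Exposure | Sequence and total |
| SAP 12.7.2 | ECG | Sequence and overall |

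The ECG entry departs from three general rules without a recorded reason.

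**2. What the cells contain**

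Let m be a common mean, d1 and d2 the day effects and t the effect of LAT8881 against placebo. Assume no carry-over and that everyone contributes to both days.

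| Sequence | Day 1 | Day 2 |
|---|---|---|
| LAT8881 then placebo | m + d1 + t | m + d2 |
| Placebo then LAT8881 | m + d1 | m + d2 + t |

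**3. Days shown separately**

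- The four sequence-by-day cells are exactly the four treatment-within-period cells under other labels. Between sequences, the Day 1 difference is t and the Day 2 difference is −t, so a reader can recover the contrast.
- The overall column does not show it. With the 10 and 10 of SAP 2.2, the Day 1 overall mean is m + d1 + (10/20)t = m + d1 + t/2, and the Day 2 overall mean is m + d2 + t/2. Each is half LAT8881 and half placebo.
- What is missing is the pooled pair of treatment columns. With n1 and n2 participants in the two sequences, that pair differs by t + (n1 − n2)(d1 − d2)/(n1 + n2), which equals t when n1 = n2. If the 17 completers expected in SAP 2.5 split 8 and 9 (an assumption), it would be t + (d2 − d1)/17.

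**4. Days combined**

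- Each sequence column averages to m + (d1 + d2)/2 + t/2. The difference between the columns is 0 whatever t is, and the overall column has the same mean.
- SAP 12.7.2 does not say which row layout it means. SAP 3.2.6 does combine Day 1 and Day 2 in each timepoint row, but it pairs those rows with treatment columns. No section combines days under sequence columns.

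**5. Maximum-shift table**

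SAP 3.2.1 sets a baseline for each period, SAP 3.2.2 defines change within each period, and SAP 3.2.6 assigns treatment to records by period. The ingredients are in place. The ECG paragraph only fails to say that the shift is taken within a period and shown by treatment.

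**The case against.** The strongest reply is that little is lost in practice. SAP 3.2.6 and SAP 12.2 already require display by treatment and could be read as governing ECG. The wording may be shorthand for treatment nested in sequence, as used for adverse events. SAP 3.2.4 says that outputs follow mock tables, which are not among the documents and may already carry treatment columns. Protocol 9.6.7 asks only for ECG summaries by timepoint. All of this is possible, but 12.7.2 is the specific text, it says something else twice, and a programmer could properly follow it. The conflict in wording stands; what the finished tables would look like is less certain.

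A reader might infer more than the documents support.

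- *That the treatment contrast is lost outright.* This is so only if days are combined under sequence columns, which no section says.
- *That precision suffers because the cells are small.* With separate days, the sequence-by-day cells are the same size as the treatment-within-period cells that protocol 21.1 requires, so small cells cannot be charged to 12.7.2.
- *That ECG is the only safety item shown by sequence.* Exposure, which protocol 21.3 lists with the safety measurements, is also summarised by sequence and total in SAP 3.2.6.
- *That a clinically significant ECG signal would be hidden.* Protocol 20.7.1 requires clinically significant ECG abnormalities to be recorded as adverse events. The SAP 12.1 overview is by treatment, and SAP 3.2.6 sets event-based tables by treatment.
- *That the shift table is a defect of the same kind.* It names no columns, so it contradicts nothing, and the laboratory shift paragraph in SAP 12.3.2 is equally silent.

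**Conclusion.** The point holds as an internal conflict with a limited consequence. Followed literally, 12.7.2 gives no LAT8881 column and no placebo column for Part B ECG values, changes from baseline or abnormal findings, contrary to protocol 21.1 with 21.3, SAP 3.2.6 and SAP 12.2, and SAP 2.5 does not record the departure.

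With separate day rows, the loss is the pooled comparison by treatment. With combined rows, it would be the whole contrast, but that layout is not specified. In either case the effect reaches only descriptive tables of ECG intervals and of findings that are not clinically significant. The ECG listings keep the raw data, grouped by sequence, and the stopping criteria in protocol 17.2 rest on adverse events, not on these tables.

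The algebra assumes no carry-over and complete data in both periods. The half-and-half mix rests on the planned 10 and 10. The actual split in the Safety Population, on which ECG is analysed, is not given, and the 17 in SAP 2.5 are expected completers, which need not be the same set. The mock tables were not available.

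**What to change.** In SAP 12.7.2, replace the Part B grouping in both sentences: present ECG values, changes from period baseline and abnormal findings by treatment within period and by treatment overall, at each timepoint, in line with protocol 21.1 and SAP 3.2.6. If a sequence split is also wanted, say that treatment is shown within sequence, as SAP 12.1 does. If sequence columns alone are deliberate, record and justify that in SAP 2.5.

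As a clarification, add that the Part B ECG maximum-shift table is built separately for each period, from that period's baseline and results (SAP 3.2.1 and 3.2.2), and shown by treatment. SAP 3.2.6 already places Day 9/ETV under total only.

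The cost is two reworded sentences, one added sentence and a check of the table shells. No new data or derivations are needed, because period baselines and the assignment of treatment by period are already defined.

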13. HANDLING OF MISSING DATA

Only recorded data will be analysed/presented and any subjects who have missing data will only have observed data reported, with no imputation for missing data.

14. CHANGES AND CLARIFICATIONS TO THE PLANNED ANALYSIS

Any changes to the statistical analysis plan will be described and justified in the final report.

15. INTERIM ANALYSES

In Part B, a blinded interim analysis was undertaken after 14 subjects have completed both periods. Enrolment will continue while the interim analysis is undertaken.

The interim analysis was to be done in two parts. Initially, 6 tables comprising a listing and table for separately for pain assessment score for pain at rest and pain following leg raise; a listing and summary table for patients general impression of change, will be developed.

In addition, the pain scores will be summarised graphically as follows:

- Figure 1: Group mean VAS scores at Rest by timepoint, two sequences combined (one panel only)
- Figure 2: Group mean VAS scores at Rest by timepoint and by sequence (left panel Treatment A then Treatment B, right panel Treatment B then Treatment A)
- Figure 3: Group mean VAS scores following leg raise by timepoint, two sequences combined (one panel only)
- Figure 4: Group mean VAS scores following leg raise by timepoint and by sequence (left panel Treatment A then Treatment B, right panel Treatment B then Treatment A)

All analyses had subject numbers assigned randomly and treatment sequence labelled A and B to maintain blind. The results were used to make an initial futility assessment. If the decision is made to proceed then, secondly, the full interim analysis was to be completed as per full listings and tables within this document.

The DSMC team will provide additional insight regarding potentially stopping the study for futility. Details will be provided in the DSMC charter.

16. SOFTWARE

The following software will be used to perform the statistical analyses: Statistical Analysis System (SAS[®]) Version 9.4 or higher (SAS Institute, Cary, North Carolina, USA).

